## 8.2 Discussion of Trial Design, Including the Choice of Control Groups

[figure not shown]
As detailed in [Section 8.1](#), this is a 48-week, prospective, randomized, multicenter, split-face, active-comparator, blinded [REDACTED] trial designed to establish that Radiesse is safe and effective for the correction of moderate to severe NLFs by demonstrating non-inferiority to Restylane and by comparing the safety profiles of both products.

Active-controlled clinical studies are considered the standard for clinical investigations whenever proven effective treatments exist on the market for a given condition. A previous study of Radiesse with active HA comparators has demonstrated effectiveness and patient satisfaction for CaHA filler compared to HA in the treatment of NLFs [17]. Restylane will be utilized as the comparator in this proposed trial, as no other CaHA filler is currently marketed in China, and Restylane represents the best possible comparator.

[REDACTED] he trial duration of 48 weeks also represents a reasonable timeframe to assess delayed-onset and/or long-term AEs.

Since subject satisfaction is the primary goal of aesthetic medicine, subjects may undergo a touch-up treatment after initial injection to achieve optimal correction [REDACTED]

[REDACTED] herefore, the choice of active comparator is suitable for demonstration of treatment effectiveness.

## 9 TRIAL POPULATION AND RESTRICTIONS

### 9.1 Number of Subjects and Sites

Approximately 118 subjects will be randomized at up to seven investigative sites in China. Enrolled subjects will sign and date the ICF before any trial-related procedures are undertaken. At each of seven sites, the number of subjects treated should not exceed 20 to ensure a reasonable distribution of subjects across all investigative sites (see [Section 13.1.2](#) for additional information).

Any treated subject who does not complete the trial will not be replaced.

Additional information regarding the estimation of sample size, including the numbers of randomized subjects projected for trial sites, is reported in [Section 13.1](#). Further information related to subject randomization is provided in [Section 13.2](#).

### 9.2 Selection of Subject Population

Assessment for eligibility criteria is based on the subject's medical records, an interview with the candidate subject, and investigator judgment. Selection criteria have been chosen to identify a suitable subject population to investigate the trial objectives and to minimize safety concerns in this population.

#### 9.2.1 Inclusion Criteria

[figure not shown]
To be eligible for trial participation, each subject must meet all of the following criteria at screening (V1; Day -10 to 1) and/or baseline (V2; Day 1):

- Has symmetrical NLFs, with the same WSRS score of 3 or 4 (moderate or severe) for both right and left NLFs [REDACTED].
- Is  $\geq 22$  and  $\leq 65$  years of age.
- Is willing to abstain from all other aesthetic treatments on ANY part of the face, including but not limited to injectable fillers, implants, neurotoxin, skin peels, laser treatments, surgical treatments, etc. for the trial's duration.

[figure not shown]

### 9.2.2 Exclusion Criteria

Subjects meeting any of the following criteria at screening (V1; Day -10 to 1) and/or baseline (V2; Day 1) are not eligible to participate in the trial:

[figure not shown]
- Has an acute inflammatory process or active infection at the injection site (e.g., skin eruptions such as cold sores, cysts, pimples, acne, rosacea, eczema, rashes, hives, or abscesses).

[figure not shown]

[figure not shown]
[figure not shown]
- Has received mid- and/or lower-facial region treatments with any dermal fillers [redacted].

- Has received facial dermal therapie [redacted].

[figure not shown]
- Had prior surgery in the mid- and/or lower-facial area, including the NLFs, or has a permanent implant or graft in the mid- and/or lower-facial area that could interfere with effectiveness assessments. [redacted]

#### **9.2.4 Subject Enrollment and Randomization**

Subjects are considered to be enrolled once the ICF is signed and dated. Eligible subjects will be randomized at baseline (V2).

Screen failures are defined in [Section 9.2.5](#).

#### **9.2.5 Screen Failures**

Subjects who provide informed consent but who do not meet eligibility criteria or who withdraw consent prior to being randomized will be defined as screen failures. The investigator will maintain all source documentation for all subjects who are considered screen failures. Minimal information will be collected in the electronic data capture (EDC) system for screen failures, such as date of informed consent, demographics, and reason for screen failure. Individuals who do not meet the criteria for participation in this trial (i.e., screen failure) may not be rescreened.

## **9.2.6 Removal of Subjects from Therapy or Assessment**

### **9.2.6.1 Treatment Discontinuation**

In the current trial design, potential reasons for discontinuation of treatment may include refusal by the subject to receive a required or recommended touch-up injection (i.e., necessary to achieve optimal correction) or a treating investigator's decision that the risk of continued treatment (i.e., touch-up injection) is greater than the subject's potential benefit.

If treatment is discontinued, the investigator will record the reason for treatment discontinuation in the trial records. The investigator may request that a subject discontinuing treatment continue to participate in the trial and complete all remaining visits and assessments for safety follow-up. For subjects who decline to continue trial participation after treatment discontinuation, additional information regarding subject withdrawal is provided in [Section 9.2.6.2](#).

### **9.2.6.2 Subject Withdrawal or Discontinuation**

Each subject will be followed to the end of trial, or until the sponsor decides to terminate the trial, whichever comes first. The only reasons a subject will not be followed for all scheduled visits include withdrawal of consent, continuous noncompliance with protocol requirements, or loss to follow-up (e.g., moving away from trial site; unresponsive to attempts to contact the subject). Additionally, the investigator can discontinue any subject, at any time, if medically necessary.

A subject has the right to withdraw from the trial at any time at his/her own request without any penalty or loss of benefits to which the subject is otherwise entitled. In cases of withdrawn consent, data collected until the date consent was withdrawn will be analyzed as recorded.

If a subject does not attend a required trial visit, the following actions will be taken:

- The site will make every reasonable attempt to contact the subject and reschedule the missed visit as soon as possible. Every effort to regain contact with the subject will be made (e.g., phone contact on different dates/times, registered mail). All contact attempts will be documented.
- If attempts to contact the subject are not successful, the subject will be considered lost to follow-up and discontinued from the trial.

The reason for the subject's discontinuation should be documented in the electronic case report form (eCRF). The investigator should make every attempt to complete the recommended follow-up assessments specified for the End of Trial (EOT) visit specified in the Schedule of Events ([Section 11.1](#) XXXXXXXXXX) while fully respecting the subject's rights. If appropriate, according to local regulations, IEC/IRB and Competent Authorities should be informed.

If a non-serious AE is unresolved at the time of the subject's final trial visit, an effort will be made to follow the subject until the AE is resolved or stabilized, the subject is lost to follow-up, or some other resolution of the event occurs. The investigator should make every attempt to follow all SAEs/unanticipated serious adverse device effects (USADEs) to resolution. Information on pregnancy and the outcome for any female who becomes pregnant during the trial will be collected.

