#### 13.1.1 Safety

The safety aim of the trial is to generate a database with short-term and sufficient long-term safety data. Based on the International Council on Harmonization of Technical Requirements for Registration of Pharmaceuticals for Human Use (ICH) E1 guideline, 100 subjects treated and observed over 48 weeks is deemed sufficient. [REDACTED]

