#### 13.1.2 Effectiveness

The sample size considerations for the primary effectiveness endpoint (i.e., change from baseline to Week 24 after last injection on the WSRSS [REDACTED]) are based on the following:

- Type I error,  $\alpha = 0.05$  (two-sided) and
- Non-inferiority margin of 0.5.

When using the 118 subjects randomized for safety and applying a drop-out rate of 15% from randomization to the Per Protocol Set (PPS), [REDACTED], 100 subjects would be available for analysis of the primary effectiveness endpoint on PPS.

For analysis on the Full Analysis Set (FAS) even more subjects are expected. [REDACTED]

To ensure a reasonable number of subjects is enrolled per investigative site, the number of subjects treated at each site should not exceed 20 in case of seven recruiting sites, 24 in case of six recruiting sites, and 28 in case of five recruiting sites.

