### 13.3 Populations for Analysis

The following analysis sets will be defined:

- The randomized set is defined as all subjects randomized into the trial.
- The Safety Evaluation Set (SES) is defined as all subjects who are randomized and receive investigational product at least once.
- The FAS is defined as all subjects who are randomized, receive investigational product, and have at least one after-baseline effectiveness assessment.
- The PPS is the subset of subjects in the FAS who have no major protocol deviations or other events that impact analysis of the primary effectiveness endpoint. Final determination of which events lead to exclusion from PPS will be made prior to database close.

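### Protocol 9.2.6.2 lets scheduled follow-up end for undefined noncompliance, or when contact fails after any one missed visit, so some obtainable Week 24 and Week 48 assessments may be forgone

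*Protocol*

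**What the plan says.** Protocol 9.2.6.2 makes follow-up to the end of the trial the default. It then gives the only reasons for not following a subject through all scheduled visits: "withdrawal of consent, continuous noncompliance with protocol requirements, or loss to follow-up". The investigator may also discontinue a subject when that is medically necessary. Continuous noncompliance is not defined, and moving away from the site is given as an example of loss to follow-up.

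The same section sets out what happens after a missed visit. Missing any required visit obliges the site to try to reach the subject and rebook, for instance by calls on different dates and by registered mail, and to document every attempt. If this fails: "If attempts to contact the subject are not successful, the subject will be considered lost to follow-up and discontinued from the trial". The text gives no minimum number of attempts, no time window, no renewed attempt at a later visit and no rule for a subject who comes back.

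At discontinuation the investigator is to try to complete the end-of-trial (EOT) assessments, and section 11.1 repeats this. Section 11.1 places the primary endpoint visit at Week 24 ± 7 days and the EOT visit at Week 48 ± 7 days, both after the last injection.

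On numbers, section 9.1 says "Approximately 118 subjects will be randomized at up to seven investigative sites in China" and that treated non-completers are not replaced. Section 13.1.1 says "100 subjects treated and observed over 48 weeks is deemed sufficient". Section 13.3 limits the PPS to FAS subjects with "no major protocol deviations or other events that impact analysis of the primary effectiveness endpoint".

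**The concern.** Both exits can end observation of someone who could still be assessed.

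- **Noncompliance.** Injections take place on Day 1, with an optional touch-up at Week 4 (Protocol 10.5.2). After that, complying means mainly attending visits and avoiding other facial procedures. A subject who has broken the second requirement may be willing to attend. The plan already has a remedy for such a deviation, namely exclusion from the PPS. Ending the visits as well does nothing for the PPS analysis and removes data from the FAS and the safety follow-up.
- **Failed contact.** One missed visit at any point can lead to discontinuation, even when the endpoint visits are months away.

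Elsewhere the protocol separates treatment from observation. Under 12.5 a pregnant subject gets no further injection but stays in the trial. Under 9.2.6.1 a subject who stops treatment may be asked to complete all visits.

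What is at stake is a loss that could be related to outcome, since a subject unhappy with one fold is plausibly more likely to seek another procedure or stop attending. It would fall on three things: the FAS sensitivity analysis, the iGAIS and sGAIS proportions (analysed on observed cases, SAP 6.1.2), and the 48-week safety follow-up, which Protocol 8.2 justifies by delayed-onset and long-term events.

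**Working it through.** **The plan's own figure.** Inputs from Protocol 13.1.2: 118 randomized, 15% drop-out from randomization to the PPS, 100 evaluable.

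- 100 / (1 − 0.15) = 117.6, rounded up to 118.
- In reverse, 118 × 0.85 = 100.3, so 100.

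The figure reproduces. Section 13.1.2 accordingly states that "100 subjects would be available for analysis of the primary effectiveness endpoint on PPS".

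**Room for loss against the 48-week safety target.** 118 − 100 = 18 subjects. The documents give no rate for noncompliance or loss-to-follow-up exits. Assuming 3 to 6 subjects leave this way (3/118 = 2.5%; 6/118 = 5.1%), they use 3/18 = 17% to 6/18 = 33% of that room. This applies to the 48-week count only. A subject excluded from the PPS for noncompliance uses up the PPS allowance whether or not visits continue.

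**Timing.** Take a subject last injected on Day 1 who misses Week 4 and cannot be reached. Week 24 is then 24 − 4 = 20 weeks away and Week 48 is 48 − 4 = 44 weeks away. Under 9.2.6.2 no one need try again. For a subject removed for noncompliance, an EOT assessment falls at the time of removal. It supplies the primary endpoint only if that happens to lie within Week 24 ± 7 days, and it cannot pick up later events.

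**Possible shift in the FAS mean.** If k of 118 subjects are unobserved and their mean intra-individual difference departs from the rest by d, the observed mean is off by (k/118) × d. Assume d = 0.5 to 1 WSRS point, all 118 in the FAS, and no missing-data method recovering any of the loss.

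- Low: 3/118 × 0.5 = 0.013.
- High: 6/118 × 1 = 0.051.

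Against the margin of 0.5 these are 0.013/0.5 = 2.5% and 0.051/0.5 = 10%.

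**Power.** No SD, assumed difference or power is visible, so the plan's power cannot be reproduced. As an illustration, assume a true difference of 0 and an SD of the paired difference of 1.0 to 1.5. Power = Φ(0.5·√n/SD − 1.96).

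| SD (assumed) | n = 100 | n = 118 |
|---|---|---|
| 1.0 | 99.9% | >99.9% |
| 1.5 | 91.5% | 95.2% |

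Even keeping all 118 changes power little, and hardly at all at an SD of 1.0 or below.

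**The case against.** The strongest case on the other side has five parts.

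- A reader might infer that one missed visit removes a subject. It does not. The missed visit starts a contact and rescheduling procedure, and discontinuation follows only if that fails. This stands.
- A reader might infer that assessments are discarded. Nothing says so. EOT assessments are to be attempted, and data collected before consent is withdrawn are analysed. What may happen is that later assessments are not sought. This stands.
- Someone who cannot be reached yields no data whatever the label. That is largely true, so on this route the gain is confined to subjects who reappear or could be reached later. A subject who has moved away is a partial exception, since such a person may still be reachable and adverse events are also assessed by phone (Protocol 11.2.2.1).
- The noncompliance clause permits visits to stop and does not order it. Much continuous noncompliance would in practice be non-attendance, which deleting the phrase does not cure. This is fair, but an undefined permission can still be applied to a willing subject.
- Safety observation does not end altogether. Unresolved adverse events are to be followed (9.2.6.2), and device-related serious events after the observation period are reportable (11.2.2.1). This is correct; what is lost is routine scheduled observation.

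There is also the question whether a Week 24 score taken after another facial procedure belongs in the FAS estimate. That is an analysis decision, and it can be made either way only if the score exists.

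**Conclusion.** The point holds as a weakness in a stated exit rule. Section 9.2.6.2 may forgo some Week 24 and Week 48 assessments from reachable or returning subjects. Those affected are the FAS sensitivity analysis, the observed-case GAIS proportions and the number observed for 48 weeks, where the room is 18 subjects.

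A reader might go further and infer that the non-inferiority conclusion is at risk. The documents do not support that. The confirmatory analysis is on the PPS, from which seriously noncompliant subjects would be excluded anyway. The illustrative FAS shift of 0.01 to 0.05 is at most about a tenth of the margin, and the illustrative power barely depends on retention at an SD of 1.0 or less.

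The 3 to 6 subjects, the 0.5 to 1 point departure and the SDs are all assumptions; the true loss cannot be computed from the documents. The FAS shift also ignores any handling of missing data. Protocol 13.4.1.1 lists earlier WSRS scores among the variables of a model whose description is partly redacted, so no criticism of that method is made here. The case rests on avoidable, possibly outcome-related loss and on long-term safety observation.

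**What to change.** Amend Protocol 9.2.6.2 in two places.

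1. Remove continuous noncompliance as a reason to stop scheduled visits. Record it as a protocol deviation and handle it through exclusion from the PPS.
2. Replace the final bullet of the missed-visit procedure with a rule to this effect: *failure to reach a subject after a missed visit does not by itself end participation; contact is tried again at each later scheduled visit; a subject who returns is assessed at all remaining visits; loss to follow-up is assigned only when the Week 48 window has closed without contact.*

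Leave withdrawal of consent and the medical-necessity clause as they are. The cost is a short protocol amendment and a few extra contact attempts per missing subject, with no new visit or procedure.

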#### **9.2.6.3**      *Provision of Care for Subjects after Trial Discontinuation*

The investigator is responsible for ensuring the adequate and safe medical care of subjects during the trial. At the end of the trial or after subject discontinuation, the investigator will ensure that appropriate consideration is given to a subject's after-trial care. Subjects will be treated by their physician according to their medical condition and standard treatments in China. Additionally, the sponsor will follow all applicable local or international regulations and guidelines regarding follow-up care for subjects.

#### **9.2.7**      *Suspension or Premature Termination of an Investigative Site*

Trial participation by individual sites may be suspended or prematurely terminated by the sponsor. Reasons for the suspension or premature termination of sites include, but are not limited to, the following:

- Investigator request;
- Serious or persistent noncompliance with the protocol, local regulations, and/or Chinese GCP;
- Suspicion of fraud;
- Failure to accrue subjects at an acceptable rate; and/or
- Ethical issues.

The sponsor will provide the investigative site with written notification documenting the reason for suspension or premature termination. The sponsor will inform the responsible regulatory authority, as appropriate, and ensure the IEC/IRB is notified. If the suspension or premature termination was in the interest of safety, the sponsor will inform all other principal investigators.

In cases of temporary suspension at an investigative site, the sponsor will conduct an analysis of the reason(s) for suspension. After completing this analysis and implementing necessary corrective actions, a temporary site suspension may be lifted. The sponsor will inform the principal investigators, the IEC/IRB, and, where appropriate, the regulatory authority of the rationale, providing relevant data supporting this decision. Concurrence must be obtained from the IEC/IRB and, where appropriate, regulatory authorities before the investigative site resumes trial activities. If subjects were informed of the suspension, the principal investigator or authorized designee will inform them of the reasons for resumption.

In cases of premature termination, the investigator will conduct site-closure activities in accordance with all applicable sponsor, local, and international guidelines and regulations.

### **9.2.8 Suspension or Premature Termination of the Trial**

Should the investigator, sponsor, the NMPA, or local regulatory authorities become aware of conditions arising during the conduct of this trial that may warrant the cessation of the trial, such action may be taken. Prior to such action, consultation between the sponsor, the investigator, and, as appropriate, the NMPA and/or local regulatory authorities will occur.

Reasons for the suspension or premature termination of the trial include, but are not limited to, the following:

- Anticipated benefit cannot justify the risk;
- New scientific data do not justify a continuation of the trial;
- Determination of a potential safety risk to subjects;
- Inadequate subject enrollment;
- Decision by the regulatory authority or IEC/IRB to suspend or terminate approval/ favorable opinion for the trial; and/or
- Sponsor decision.

If suspicion of an unacceptable risk to subjects arises during the trial or if instructed by the IEC/IRB or regulatory authorities, the sponsor will suspend the trial while the risk is assessed. If the analysis determines that implementing necessary corrective actions is sufficient, a temporary trial suspension may be lifted. If an unacceptable risk is confirmed, the sponsor will terminate the trial.

If the trial is suspended or prematurely terminated for any reason, the sponsor will inform all investigators and relevant regulatory authorities promptly of the trial suspension/termination and reason for the action, as detailed in [Section 9.2.7](#). The investigator will conduct site-closure activities in accordance with all applicable sponsor and local/international guidelines and regulations.

### **9.2.9 End of Trial**

The end of the trial is defined as when the database is closed for the final (Week 48 after last injection) analyses.

## 10 TRIAL DEVICES AND TREATMENT OF SUBJECTS

### 10.1 Description of Trial Devices

#### 10.1.1 *Investigational Medical Device - Radiesse*

Radiesse injectable implant is an opaque, sterile, non-pyrogenic, semi-solid, cohesive implant. The principal component is synthetic CaHA suspended in a gel carrier that consists primarily of water. [REDACTED]

Radiesse is provided as a single use, non-pyrogenic device. Each unit contains a 1.5 mL/syringe of injection media in a pre-filled syringe. The investigational device will be supplied by the sponsor and will be marked for trial-specific clinical use only. [REDACTED]

[REDACTED] do not use if the expiration date has been exceeded. Do not re-sterilize the syringe or any of its separately packaged components (e.g., needle). In the event the package is opened or damaged, do not use and notify the sponsor immediately.

Radiesse injectable implant is indicated for subdermal implantation for the correction of moderate to severe facial wrinkles and folds, such as NLFs. [REDACTED]

